Even higher doses were administered to healthy volunteers in the FIH study (KY1005-CT01), where the top (loading) dose was 12 mg/kg, which in an 85 kg individual would equate to a single flat dose of 1,020 mg. In this study, one AE of note occurred at the top dose of systemic allergic reaction. However, this dose level was far higher than that being tested in patients in the Phase 2b study. No otherwise clinically significant AEs, SAEs or deaths occurred at any dose level in KY1005-CT01.

The total patient exposure (years) for KY1005-CT02 is 15.4 patient years for KY1005 low dose, and 16.5 patient years for KY1005 high dose. However, no safety or tolerability concerns have been identified across the clinical development programme to date, and the overall adverse event profile of KY1005 is unremarkable.

Post Week 24 period: Randomised withdrawal design to inform Phase III extended dosing interval

As part of this study, the intention is to build on the sustained clinical response observed in the Phase 2a study with an assessment of the durability of response during a 28-week withdrawal period in those patients who achieve \geq EASI 75 or who attain IGA 0/1 at Day 169 (Week 24).

		l

Loss of clinical response

Loss of clinical response is defined as the first instance of <EASI 50 during the second study period and where rescue therapy is no longer permitted as per Section 5.3.4.

If loss of clinical response occurs on or after the Day 197 (Week 28) visit, Investigators wil
be able to choose to either discontinue the patient from KY1005-CT05 (DRI17366) or to
progress to the LTE study (LTS17367, LTE).

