3.2.1 Study flow

The overall study design is presented in Figure 3-1.

1-Mar-2022 Version number: 1

Figure 3-1: Overall StudyDesign

AD=atopic dermatitis; IMP=investigational medicinal product; EP=endpoint; EASI=eczema area and severity index; IGA= investigator global assessment; LTE=long-term extension; Q4W=every 4 weeks; NA=not applicable.

- a On Day 169 (Week 24), patients are re-randomised prior to IMP administration on the basis of their Day 169 (Week 24) response.
- Patients initially enrolled at Baseline into the Placebo, 62.5 mg, 125 mg and 250 mg KY1005 treatment arms who do not achieve ≥ EASI 75 or IGA0/1 at Day 169 (Week 24) will have the opportunity to receive KY1005 Q4W from Day 169 (Week 24) by enrolling in a long-term extension (LTE) study (LTS17367 LTE). Participation in the LTE is subject to meeting the inclusion/exclusion criteria. Any patient who in the Investigator's opinion should not be enrolled into the LTE, or where the patient declines further participation will have an additional 112 days safety follow-up from Day 141 (Week 20) and then be discharged from the study.
- c Patients who achieve ≥ £ASI 75 or who attain IGA0/1 at Day 169 (Week 24), irrespective of their Baseline group will be randomised 3:1 to either enter a maintenance withdrawal phase or continue on their pre-Week 24 dose/interval.

- d If loss of response from Day 197 (Week 28) occurs between visits and retreatment with KY1005 is considered appropriate, patients will be permitted to move to the LTE (subject to meeting the inclusion/exclusion criteria for the LTE). Loss of clinical response is defined as < EASI 50 during the second study period and where rescue therapy is no longer permitted as per Section 5.3.4. Patients who in the Investigator's opinion should not be enrolled into the LTE, or where the patient declines further participation, will enter safety follow-up.
- e Patients who are responders at Day 169 (Week 24) and complete the second study period to Day 365 (Week 52) without loss of clinical response will enter safety follow-up. If during safety follow-up or after end of study the patients experience worsening of their AD, and in the investigator's opinion re-treatment with KY1005 is considered appropriate, they may be considered for enrolment in the LTE (subject to meeting inclusion/exclusion criteria).

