3.4 Definition of End of Study

The EOS is defined as the last patient undergoing the last visit of the study. This will either be:

• Day 169 (Week 24) (or earlier termination) for those patients who do **not** achieve ≥ EASI 75 or IGA 0/1 at Day 169 (Week 24), and are subsequently enrolled in the LTE;

Or

• Day 281 (Week 40) (or earlier termination) for those patients who do **not** achieve ≥ EASI 75 or IGA 0/1 at Day 169 (Week 24), and are **not** enrolled in the LTE and have additional safety follow-up to a total of 140 days after the last dose of IMP;

Or

Day 365 (Week 52) (or earlier termination) for those patients who achieve ≥ EASI 75 or who attain IGA 0/1 at Day 169 (Week 24) and continue on either their pre-Week 24 dose/interval or enter the withdrawal arm, experience loss of clinical response at or after Day 197 (Week 28) and are enrolled in the LTE. Those patients not enrolled in the LTE will have additional safety follow-up to a total of 140 days after the last dose of IMP;

Or

• Day 477 (Week 68) (or earlier termination) for those patients who reach Day 365 (Week 52), are still considered to be responding to study treatment, and are **not** enrolled in the LTE and have additional safety follow-up to a total of 140 days after the last dose of IMP.

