3.5 Early Study Termination

The study can be terminated at any time for any reason by the Sponsor (including approval or the favourable opinion is revoked, in the event of a negative change in the benefit/risk ratio when the necessary adjustment to the maximum sum insured is not possible; failure to enrol; futility; safety decision etc). If the trial is suspended or terminated early, the Investigator will promptly inform the trial patients and should assure appropriate therapy and follow-up.

No further IMP will be given to a patient if any study permanent discontinuation rules are met (see Section 9.1), including recommendation of the Independent Data Monitoring Committee (IDMC; Section 3.8). If a patient withdraws from the study treatment early but consent is retained, study assessments may be continued until a) Day 169 (Week 24) for patients who withdraw from study treatment during the first study period and therefore are **not** eligible for

Version number: 1

1-Mar-2022

LTE, or b) until Day 365 (Week 52) or the end of the safety follow-up period in patients who withdraw from study treatment after Day 169 (Week 24).

Unless patients continue in the LTE at Day 169 (Week 24) or due to loss of clinical response at or after Day 197 (Week 28), a safety follow-up for 140 days after the last dose of IMP will be required.

In addition, the Investigator may withhold further IMP from a patient if they report moderate-or-severe (regardless of seriousness) adverse reactions which are attributed to the IMP. There will be no obligation to unblind treatment allocation in making this decision.

The Sponsor may discontinue the entire study at any time based on information received during the running of the study that demonstrates an unexpected risk or absence of benefit to patients. This may for example follow the request of the IDMC or where additional information emerges either during the study or from other sources (eg, literature or Health Authorities).

If the study is discontinued, where patients withdraw early or where IMP has been discontinued by the Investigator, patients will be required to be followed-up for a minimum of 140 days for safety evaluation.

Further details of IMP discontinuation are provided in Section 9.1.

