6 STUDY PROCEDURES

6.1 Study Schedule of Assessments

The schedule of procedures and assessments during the study is summarised and presented in Table 6-1, Table 6-2 and Table 6-3 for all patients, plus Table 6-4 for patients who are not enrolled into the LTE and have additional safety follow-up. Where possible, the patient reported outcome (PRO) assessments completed at the study site are to be completed by patients prior to the completion of other study assessments and the administration of study drug.

1-Mar-2022

Version number: 1

In general, and wherever possible, patients will be assessed at the approved study clinics/facilities. Section 17.14 (Appendix 14) details contingency procedures that are suggested for a regional or national emergency declared by a governmental agency that prevents access to the study site, to ensure the safety of the patients, to consider continuity of the clinical study conduct, protect trial integrity, and assist in maintaining compliance with GCP in Conduct of Clinical Trials Guidance.

1-Mar-2022 Version number: 1

Table 6-1: Schedule of Assessments Screening to Day 113(Week 16)

Visit	1		2 ^b	3	4	5	6ª	7 ª	8ª	9ª	ET#
Visit days	-29 to -8	-7 to 1	1	8	15	22	29	57	85	113	-
Visit weeks	-4 to -1	- 1	0	1	2	3	4	8	12	16	-
Visit window (days)	0	0	0	±3	±3	±3	±3	±3	±3	±3	-
	Scree	ning	Baseline			Tr	eatment				
Description	Clir	nic	Clinic	Clinic	Clinic	Telephonem	Clinic	Clinic	Clinic	Clinic	Clinic
Informed consent	X										
Demographics	X										
Medical history	X										
Concomitant medications - including emollients	X		Xª	X	X	X	X	X	X	X	X
AEs (including SAEs)	<====									===>	X
Inclusion/exclusion criteria	X		X								
Physical examination	X		X		X		X	X	X	X	X
Body weight and height (height at Screening only)	X		X							X	X
Vital signs ^c	X		X				X	X	X	X	X
12-lead ECG	X		X					X		X	X
EASI	X		X		X		X	X	X	X	X
BSA	X		X		X		X	X	X	X	X
IGA	X		X		X		X	X	X	X	X

1-Mar-2022 Version number: 1

Visit	1		2 ^b	3	4	5	6 ^a	7 ª	8 ^a	9 ^a	ET#
Visit days	-29 to -8	-7 to 1	1	8	15	22	29	57	85	113	-
Visit weeks	-4 to -1	- 1	0	1	2	3	4	8	12	16	-
Visit window (days)	0	0	0	±3	±3	±3	±3	±3	±3	±3	-
	Screening		Baseline	Treatment							
Description	Clinic		Clinic	Clinic	Clinic	Telephonem	Clinic	Clinic	Clinic	Clinic	Clinic
SCORAD Index ¹	X		X				X	X	X	X	X
DLQI			X		X			X		X	X
ADCT ¹			X							X	X
HADS ¹			X					X		X	X
Blood samples for virology (HIV, Hepatitis B and C) and TB (QuantiFERON®-TB Gold blood test) ⁿ	X										

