ADAs=anti-drug antibodies; ADCT=atopic dermatitis control tool; AEs=adverse events; BSA=body surface area; DLQI=Dermatology Quality of Life Index; EASI=Eczema Area and Severity Index; ECG=electrocardiogram; FBC=full blood count; IgE=immunoglobulin E; IMP=Investigational Medicinal Product; NRS=Numerical Rating Scale; POEM=Patient Oriented Eczema Measure; PK=pharmacokinetics; PRO=patient reported outcome; SAE=serious adverse event; SCORAD=SCORing of Atopic Dermatitis; IGA= Investigator Global Assessment; HADS= Hospital Anxiety and Depression Scale.

- # Early Termination could be done by the Sponsor or the Investigator (see Section 3.4, Section 3.5 and Section 9).
- a On IMP administration days in this time period, all assessments, including taking blood samples, will be performed pre-injection unless stated otherwise.
- b On IMP administration days in this time period, vital signs will be measured pre-injection and 30 minutes post- injection. The tolerance on vital signs after dosing is ±5minutes.
- d NRS (pruritus) will be recorded daily, ideally in the morning, based on the previous 24 hours with worst (maximum) itch intensity recorded.
- f A telephone visit is defined as a videoconference, video call or telephone call.
- g Where possible, the PRO assessments completed at the study site are to be completed by patients prior to the completion of other study assessments and the administration of IMP.
- If urine pregnancy test is positive, a serum control must be done before IMP administration.

The ICF from the DRI/Phase2b/parent study will not be valid as LTE informed consent. In order for patients to roll over to the LTE a specific LTE ICF will need to be applied, agreed upon and signed at the LTE study, as the LTE is a separated protocol.

Table 6-4: Schedule of Assessments - SafetyFollow-up

Visit	29 ^a	30 ^a	31ª	32ª	
Visit days	393	421	449	477	F/D#
Visit weeks	56 ^d	60 ^d	64 ^d	68 ^d	ET#
Visit window (days)	±7	±7	±7	±7	
Description	Clinic	Telephone ^b	Clinic	Clinic	Clinic
Concomitant medications - including emollients	X	X	X	X	X
AEs (including SAEs)	÷				X
Physical examination			X	X	X
Vital signs	X		X	X	X
12-lead ECG	X		X	X	X
Safety tests (FBC, non-fasting biochemistry, electrolytes, urinalysis)	X		X	X	X
Pregnancy test – females only (urine) ^c	X		X	X	X
Blood samples for serum concentrations of ADAs					

ADA=anti-drug antibody; AEs=adverse events; ECG=electrocardiogram; FBC=full blood count; SAE=serious adverse event.

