6.4.4 Standard Laboratory Safety Tests

All standard safety laboratory parameters assessed will be evaluated centrally.

The standard laboratory safety tests consisting of haematology (full blood count [FBC]), clinical chemistry (electrolytes and non-fasting biochemistry) and urinalysis assessments defined in Table 6-5 will be performed throughout the study.

All WOCBP will also have a serum pregnancy test at Screening. Urine pregnancy tests will be performed pre-injection on IMP administration days, and at the early termination visit, Days 393 (Week 56), 449 (Week 64), and 477 (Week 68) of the safety follow-up period. These will be performed locally. If a urine pregnancy test result is positive, it must be confirmed by a serum pregnancy test.

For post-menopausal women only, a blood sample will also be taken at Screening for FSH.

Screening laboratory assessments may be repeated a maximum of once where initial results are in the Investigator's opinion, clinically significant and only provided the initial result is considered a temporary anomaly and there is a documented explanation as to the likely cause of the result (Section 4.6).

All laboratory reports should be reviewed, signed, and dated by a designated physician within 24 hours of receipt. These will be checked and verified by the Study Monitor during monitoring visits.

[figure not shown]
Table 6-5: Standard Laboratory SafetyTests

Category	Parameter
Haematology	WBCC and differentials, RBCC, RDW, Hb, HCT, nucleated red blood cells, platelet count, MCH, MCHC, MCV, and MPV
Clinical chemistry	Albumin, sodium, potassium, chloride, bicarbonate, urea, creatinine, glucose, calcium, phosphate, ALT, AST, GGT, LDH, alkaline phosphatase, total protein, iron, total bilirubin and CPK
Urinalysis	pH, protein, glucose, ketones and blood

ALT=alanine aminotransferase; AST=aspartate aminotransferase; CPK=creatine phosphokinase; GGT=gamma-glutamyl transferase; Hb=haemoglobin; HCT=haematocrit; LDH=lactate dehydrogenase; MCH=mean cell haemoglobin; MCHC=mean cell haemoglobin concentration; MCV=mean cell volume; MPV=mean platelet volume; RBCC=red blood cell count; RDW=red cell distribution width; WBCC=white blood cell count.

Assay methodology and procedures will be described in a laboratory manual to be finalised before the samples are collected. Samples will be shipped to and analysed by PPD Central Laboratory.

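### Table 6-4 fixes safety follow-up on Days 393 to 477, so patients outside the LTE who stop early can have no scheduled visit in their required 140 days; footnote b of Figure 3-1 also conflicts with Section 3.4

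*Protocol*

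**What the plan says.** The length of follow-up is clear. Protocol 3.4 says of second-period patients who lose response: "Those patients not enrolled in the LTE will have additional safety follow-up to a total of 140 days after the last dose of IMP". Protocol 3.5 says more generally that, unless the patient continues in the LTE, "a safety follow-up for 140 days after the last dose of IMP will be required". Footnote d of Figure 3-1 sends patients who lose response and stay out of the LTE into this follow-up: "Patients who in the Investigator's opinion should not be enrolled into the LTE, or where the patient declines further participation, will enter safety follow-up".

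The visits are set in Section 6.1, which gives Tables 6-1 to 6-3 for everyone, "plus Table 6-4 for patients who are not enrolled into the LTE and have additional safety follow-up". Table 6-4 has visits on Days 393, 421 (telephone), 449 and 477, each ±7 days. Footnote a to the table confirms that it is for patients not in the LTE who need more safety follow-up. None of its visible footnotes ties the days to the last dose. Section 6.4.4 places the follow-up urine pregnancy tests on "Days 393 (Week 56), 449 (Week 64), and 477 (Week 68) of the safety follow-up period", besides the early termination visit. SAP Table 9 repeats the same days.

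For Week 24 non-responders who do not enter the LTE, footnote b of Figure 3-1 says they "will have an additional 112 days safety follow-up from Day 141 (Week 20) and then be discharged from the study". Section 3.4 gives Day 281 as the end of study for the same patients.

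**The concern.** The required period moves with the last dose, but the visits meant to fill it do not. A patient whose dosing stops early can complete the 140 days before the first Table 6-4 visit falls due. That patient then has an early termination visit (9.2) and an end-of-study visit that 3.4 defines but no schedule table places. No safety laboratory test, ECG, vital sign or pregnancy test is scheduled between the two.

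This matters because TEAE incidence is the primary safety endpoint (protocol 10.4.2.4.1). The SAP's treatment-emergent period runs to 140 days after the last dose (SAP 9.1). Its analyses of potentially clinically significant abnormalities take the worst value in that period, safety follow-up visits included (SAP 9.2). Pregnancies are reportable for 5 months after the last dose (protocol 8.3.1). Without a usable schedule, the timing of these checks is left to each site.

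**Working it through.** **Inputs.** Follow-up of 140 days after the last dose (3.4, 3.5). Second-period doses on Days 169, 197, 225, 253, 281, 309 and 337 (5.2.1, Table 6-3). Assessments precede injection (Table 6-3, footnote a). Table 6-4 visits on Days 393, 421, 449 and 477, ±7, so the earliest possible visit is Day 393 − 7 = 386.

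**The plan's own end days.** Week 52 completers: 337 + 140 = 477, and 365 + 112 = 477. Week 24 non-responders outside the LTE: 141 + 140 = 281, and 169 + 112 = 281. Both agree with 3.4.

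**Which last dose Table 6-4 fits.** 393 − 337 = 56, 421 − 337 = 84, 449 − 337 = 112, 477 − 337 = 140. The visits are therefore at 56, 84, 112 and 140 days after a last dose on Day 337, and after no other.

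**Loss of response found at visit L.** If the dose is withheld, the last dose is L − 28 and the end is L + 112. If the dose is given, the end is L + 140.

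| Loss found (Day) | Last dose if withheld | End | Table 6-4 visits by the end | End if dosed that day | Table 6-4 visits by the end |
|---|---|---|---|---|---|
| 197 | 169 | 309 | 0 | 337 | 0 |
| 225 | 197 | 337 | 0 | 365 | 0 |
| 253 | 225 | 365 | 0 | 393 | 1 |
| 281 | 253 | 393 | 1 | 421 | 2 |
| 309 | 281 | 421 | 2 | 449 | 3 |
| 337 | 309 | 449 | 3 | 477 | 4 |

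The visit windows do not rescue the first three rows. With the dose withheld and the last dose given 3 days late, the latest end is 365 + 3 = 368, still before Day 386. A loss noticed between visits, from Day 197 up to the Day 253 dose, has a last dose no later than Day 225, so the result is the same.

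**Length of the gap.** With the dose withheld, the exit visit is 28 days after the last dose. That leaves 140 − 28 = 112 days, or 112/140 = 80% of the period, with no scheduled contact before the end-of-study visit.

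**Same patients on the 9.1.3 route.** After a loss on Day 197 with the dose withheld, Table 6-3 visits on Days 225, 253, 281 and 309 fall inside the period: 4 visits. Continuing through Table 6-3 and then Table 6-4 gives 4 visits for every row with the dose withheld, and 5 if dosed.

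**Part 1.** Last dose on Day 1, 29, 57, 85, 113 or 141 gives an end on Day 141, 169, 197, 225, 253 or 281. No Table 6-4 visit falls inside any of these. Continued attendance under 9.1.3 runs only to Day 169 for this group. It covers the whole period for a last dose on Day 1 or 29, but leaves up to 281 − 169 = 112 days uncovered for a last dose on Day 141, which is the case of the Week 24 non-responder.

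**Footnote b.** 141 + 112 = 253, against 281 in 3.4: a difference of 28 days, 28/140 = 20%. Counting the same 112 days from Day 169 gives 281.

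**The case against.** The strongest reply is that the protocol already provides for these patients. Section 9.1.3 encourages anyone who stops treatment to complete the remaining visits. It expressly covers those who stop after Day 169 and do not or cannot enter the LTE, with visits to Day 365. Sections 3.5 and 5.3.4 say much the same. Section 6.1 adds Table 6-4 to Table 6-3 and does not replace it. This stands for second-period patients who keep attending. It does not close the gap, because continuation is optional. Those who decline are sent by 9.1.3 to safety follow-up under the Section 6.1 schedule, where the follow-up visits are those of Table 6-4. Week 24 non-responders have no such route past Day 169.

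Stronger readings are tempting, and the documents do not support them:

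- **Follow-up is cut short or TEAEs are lost.** Sections 3.4, 3.5 and 8.1 keep the 140 days. Adverse events are collected to the last visit (6.4.3), and SAEs and AESIs are reported within 24 hours of the site learning of them. What is missing is a set of visit dates.
- **The gap biases Part 2 safety comparisons.** That would need more early exits outside the LTE in one arm, and no rate is given. Withdrawal-arm patients had their last possible active dose on Day 141. At exit on Day 197 they are already 197 − 141 = 56 days past it, and later exits are further still. For them the 140 days count from a placebo injection.
- **About 105 of 350 patients are affected.** That figure is the 30% drop-out to Day 169 in 3.6 (0.30 × 350 = 105). It concerns Part 1 and includes patients who withdraw consent, are lost, or keep attending. Section 1.5.3 uses about 20%, which gives 70. Neither figure counts the patients at issue.
- **Footnote b discharges patients 28 days early by design.** Since 112 days from Day 169 gives exactly the Day 281 of 3.4, a wrong anchor day is the likelier explanation.

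Parts of 3.1 and 3.2 are blacked out, and Figure 3-1 itself is not shown. Whether the hidden text mentions the off-treatment route cannot be checked. The lettered footnotes of Table 6-4 are visible and contain no rule relative to the last dose.

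**Conclusion.** Wrong as written; minor. Table 6-4 and 6.4.4 fit only a last dose on Day 337. For patients outside the LTE who do not take the optional visits under 9.1.3, no Table 6-4 visit falls within the required 140 days if loss of response is found on Day 197, 225 or 253 and that day's dose is withheld. For Days 197 and 225 this holds even if the dose is given. Week 24 non-responders and patients who stop in Part 1 also have none. From Day 281 onward, cover rises from 1 visit to 3 with the dose withheld. Footnote b contradicts 3.4 by 28 days.

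The counts rest on the visible tables and on dosing every 4 weeks. The number of patients affected is unknown, and no effect on TEAE rates or on any efficacy endpoint is shown.

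**What to change.** 1. Head the Table 6-4 visits as 56, 84 (telephone), 112 and 140 days after the last dose, and word 6.4.4 the same way. Carry the headings into SAP Table 9. Week 52 completers stay on Days 393, 421, 449 and 477. A loss found on Day 197 (last dose Day 169) gets Days 225, 253, 281 and 309. A Week 24 non-responder with a last dose on Day 141 gets Days 197, 225, 253 and 281.
2. In footnote b, give the end as 140 days after the last dose, which is Day 281 when that dose is on Day 141.

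A cross-reference from footnote d to 9.1.3 would help readers but is optional.

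The cost is a set of column headings and a few sentences. No patient is followed beyond the 140 days already required. The study-day windows in SAP Table 14 already include these days, although its visible text lists no ECG at some of them (Week 44, for example), so that column should be checked.
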